7.1.5 Unexpected Adverse Events

An "unexpected" AE is an AE that is not listed in the IB or is not listed at the specificity or severity that has been observed. For example, hepatic necrosis would be "unexpected" (by virtue of greater severity) if the IB referred only to elevated hepatic enzymes or hepatitis. Similarly, cerebral thromboembolism and cerebral vasculitis would be "unexpected" (by virtue of greater specificity) if the IB listed only cerebral vascular accidents. "Unexpected" also refers to AEs that are mentioned in the IB as occurring with a class of drugs or as anticipated from the pharmacological properties of the drug, but are not specifically mentioned as occurring with the study drug under investigation.

7.2 DOCUMENTING AND REPORTING OF ADVERSE AND SERIOUS ADVERSE EVENTS

The investigator is responsible for ensuring that all AEs and SAEs that are observed or reported during the study, as outlined in the prior sections, are recorded on the CRFs. All SAEs also must be reported on the SAE Worksheet.

7.2.1 Adverse Event Reporting Period

The AE reporting period for this study begins when the subject takes the first dose of study drug and ends 30 days after the last dose of study drug. Ongoing AEs from parent protocol must be followed to resolution or until the investigator assesses the subject as stable, or the subject is lost to follow-up or withdraws consent. SAEs occurring after 30 days following the last dose of study drug should also be reported if considered related to study drug. If an SAE is present at the Safety Follow-up Visit, the SAE (and associated AEs and concomitant medications) should be followed to resolution or until the investigator assesses the subject as stable, or the subject is lost to follow-up or withdraws consent. Resolution/stable means the subject has returned to baseline state of health or the investigator does not expect any further improvement or worsening of the event.

If a death occurs within 30 days after the last dose of study drug the death must be reported to the Sponsor as an SAE.

7.2.2 Assessment of Adverse Events

Investigators will assess the occurrence of AEs and SAEs at all subject evaluation time points during the study. All AEs and SAEs whether volunteered by the subject, discovered by study personnel during questioning, or detected through physical examination, clinically significant laboratory test, or other means will be recorded in the subject's medical record and on the AE eCRF and, when applicable, on a SAE Worksheet.

Each recorded AE or SAE will be described by its duration (i.e., start and end dates), severity, regulatory seriousness criteria, if applicable, suspected relationship to the investigational product (see following guidance), and any actions taken.

7.2.3 Expedited Reporting Requirements for Serious Adverse Events

All SAEs (initial and follow-up information) will be reported on a SAE Worksheet and faxed to Pharmacyclics Drug Safety, or designee, within 24 hours of the discovery of the event or information. Pharmacyclics may request follow-up and other additional information from the investigator (e.g., hospital admission/discharge notes, laboratory results).

All deaths should be reported with the primary cause of death as the AE term, as death is typically the outcome of the event, not the event itself. The primary cause of death on the autopsy report should be the term reported. Autopsy and postmortem reports must be forwarded to Pharmacyclics Drug Safety, or designee, as outlined above.

If study drug is discontinued because of an SAE, this information must be included in the SAE report.

7.2.4 Events of Special Interest

Specific AEs, or groups of AEs, will be followed as part of standard safety monitoring activities by the Sponsor. These events will be reported to the Sponsor within 24 hours of awareness following the procedure described above for SAEs (Section 7.2.3) and will require enhanced data collection. All Events of Special Interest will be submitted without a serious criterion selected if no other serious criterion is met.

7.2.4.1 Major Hemorrhage

Major hemorrhage is defined as any of the following:

- Any treatment-emergent hemorrhagic adverse events of Grade 3 or higher. a.
- Any treatment-emergent serious adverse events of bleeding of any grade

- Any treatment-emergent central nervous system hemorrhage/hematoma of any grade
- a. All hemorrhagic events requiring transfusion of red blood cells should be reported as grade 3 or higher AE per CTCAE.

Events meeting the definition of major hemorrhage will be captured as an event of special interest according to Section 7.2.4 above.

7.2.5 Pregnancy

Before study enrollment, subjects must agree to take appropriate measures to avoid pregnancy. However, should a pregnancy occur, consent to provide follow-up information regarding the outcome of the pregnancy and the health of the infant until 30 days old will be requested.

A female subject must immediately inform the investigator if the subject becomes pregnant from the time of consent to 30 days after the last dose of study drug. A male subject must immediately inform the investigator if the subject's partner becomes pregnant from the time of consent to 3 months after the last dose of study drug. Any female subjects receiving PCI-32765 who become pregnant must immediately discontinue study drug. The investigator should counsel the subject, discussing any risks of continuing the pregnancy and any possible effects on the fetus.

Although pregnancy itself is not regarded as an AE, the outcome will need to be documented. Any pregnancy occurring in a subject or subject's partner from the time of consent to 30 days after the last dose of study drug must be reported. Record any occurrence of pregnancy on the Pregnancy Report Form Part I and fax to Pharmacyclics Drug Safety, or designee, within 24 hours of learning of the event. The pregnant female will be followed for outcome, which is defined as elective termination of the pregnancy, miscarriage, or delivery of the fetus. For pregnancies with an outcome of live birth, the newborn infant will be followed until 30 days old by completing the Pregnancy Report Form Part II. Any congenital anomaly/birth defect noted in the infant must be reported as a SAE.

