5.6.6 Reproductive Toxicity

Reproductive toxicity studies have not been done with PCI-32765. Therefore, women of child-bearing potential who are sexually active must use highly effective contraception during the study and for 90 days after the last dose of PCI-32765. Men who are sexually active, must use highly effective contraception during the study and for 90 days (3 months) after the last dose of PCI-32765. Subjects should promptly notify the investigator if they, or their partner, become pregnant during this period. If a female subject becomes pregnant during the treatment period, she must discontinue PCI-32765 immediately. Pregnancy in a female subject or a male subject's partner must be reported in the same manner as a SAE (refer to Section 7.2.3).

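### Pregnancy windows conflict: female notification stops at 30 days in 7.2.5 but runs to at least 90 days in 5.6.6, and 7.2.5 has partner pregnancies notified to 3 months with stated mandatory reporting only to 30 days

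*Protocol*

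**What the plan says.** **Section 7.2.5 (Pregnancy)** contains three time limits and one instruction without a limit.

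- A female subject must tell the investigator at once "if the subject becomes pregnant from the time of consent to 30 days after the last dose of study drug".
- A male subject must do so if his partner "becomes pregnant from the time of consent to 3 months after the last dose of study drug".
- Any pregnancy in a subject or a partner "from the time of consent to 30 days after the last dose of study drug must be reported".
- The next sentence tells the site to enter every pregnancy on Part I of the pregnancy form and fax it to the sponsor's drug safety group within 24 hours. It names no post-dose limit.

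**Section 5.6.6 (Reproductive Toxicity)** says that sexually active women of childbearing potential "must use highly effective contraception during the study and for 90 days after the last dose of PCI-32765", and that sexually active men "must use highly effective contraception during the study and for 90 days (3 months) after the last dose of PCI-32765". It continues: "Subjects should promptly notify the investigator if they, or their partner, become pregnant during this period". It then requires pregnancies in female subjects and in male subjects' partners to be reported like an SAE, pointing to 7.2.3, and states no window. Section 7.2.3 sets a deadline, "within 24 hours of the discovery of the event or information", but no post-dose window either.

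On a different matter, 5.6.6 opens by stating that no reproductive toxicity studies have been carried out.

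**The concern.** The two sections should tell a site the same thing about which pregnancies after treatment it must hear about, pass on and follow to outcome. They do not. A site working from 7.2.5 would ask a woman to tell it about a pregnancy up to day 30 after her last dose. A site working from 5.6.6 would ask her up to day 90 at least. Within 7.2.5, a man is asked for information for about two months beyond the point where the sentence that makes reporting compulsory stops.

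At stake is uniform collection of pregnancy exposure data in a long-term safety study of a drug for which the protocol itself (1.3.2) reports fetal loss and malformations in rats. Pregnancies arising from day 31 to about day 90 could be notified, reported and followed differently from site to site.

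**Working it through.** No power, alpha or event count is involved. The check sets the windows side by side and takes differences.

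**Inputs (days after last dose)**

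| Duty | 7.2.5 | 5.6.6 |
|---|---|---|
| Female subject notifies investigator | to 30 days | study plus 90 days |
| Male subject notifies partner pregnancy | to 3 months | study plus 90 days, equated there with 3 months |
| Site reports pregnancy, subject or partner | mandatory sentence: to 30 days; next sentence: no limit | like an SAE: no limit |

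The 90 days for notification in 5.6.6 come from "Subjects should promptly notify the investigator if they, or their partner, become pregnant during this period". The only periods named before that sentence are the two contraception periods. Inclusion criteria 2 and 3 in section 4.1 use the same lengths for contraception: 90 days for women and 3 months for men.

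**Female notification, across sections.** 90 − 30 = 60 days, that is, days 31 to 90. This is a minimum. The period in 5.6.6 also covers the time during the study. Section 3.1 counts the Follow-up Phase as part of subject participation, and 6.3.3 continues follow-up to the end of the study. On that reading the period in 5.6.6 can extend past day 90.

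**Partner pregnancies, within 7.2.5.** With 3 months taken as 90 days, as 5.6.6 does: 90 − 30 = 60 days. By calendar, three months span 89 to 92 days, so the difference is 89 − 30 = 59 to 92 − 30 = 62 days.

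These are spans of time, not estimates of events.

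**A pregnancy arising on day 60, provision by provision**

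| Provision | Female subject | Male subject's partner |
|---|---|---|
| 7.2.5 notification | outside | inside |
| 5.6.6 notification | inside | inside |
| 7.2.5 mandatory-reporting sentence | outside | outside |
| 7.2.5 next sentence (form and fax) | no limit stated | no limit stated |
| 5.6.6 reporting like an SAE | no limit stated | no limit stated |

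For the woman, the sections disagree on whether the site should be told at all. For the partner, both sections have the site told. What happens next depends on whether the 30-day sentence is taken to govern the one after it.

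**What else might catch such a pregnancy.** Pregnancy tests are scheduled only at Screening and at the Safety Follow-up Visit (6.1, Appendix 3). Later contacts, about every 3 months, list progression, new anticancer therapy and survival (6.3.2, 6.3.3), not pregnancy. After the Safety Follow-up Visit the planned route is therefore notification by the subject, which is one of the duties in conflict.

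**The opening sentence of 5.6.6.** Section 1.3.2 reports a rat embryo-fetal toxicity study with fetal loss and malformations. Section 1.3.2.1 says only that animal fertility studies were not done. The blanket denial in 5.6.6 agrees with neither.

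**The case against.** The best counter-argument is that the protocol taken as a whole already requires the reports. The sentence after the 30-day limit in 7.2.5 covers any pregnancy and has no window, and 5.6.6 adds a reporting duty with no window. A duty without a limit covers day 60. This stands. A reader might infer that a site following 7.2.5 is free not to report a day-60 partner pregnancy it has been told about. The text does not support anything that firm; it supports two readings. The opposite certainty is not available either: if the second sentence is wholly unlimited, the 30-day limit just before it has no effect.

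A second argument is that both notification rules can be obeyed together. Section 7.2.5 uses mandatory language up to 30 days, 5.6.6 uses softer language for longer, and a site that follows the wider text breaches neither. The 30 days also match the adverse event reporting period in 7.2.1. That limits the harm, but it does not explain why 7.2.5 gives women 30 days and men 3 months.

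Third, there are partial safeguards. Section 7.2.5 makes any congenital anomaly an SAE, and 7.2.1 keeps related SAEs reportable after day 30. These also stand. They would not by themselves capture a termination, a miscarriage or a normal birth, although 7.2.5 counts each of these as an outcome to be followed.

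Finally, the sentence on reproductive toxicity studies is nonclinical background. It changes no instruction and adds no weight to the point about windows.

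**Conclusion.** The inconsistency is real and minor. Female notification differs between 7.2.5 and 5.6.6 by at least 60 days. Within 7.2.5, partner notification exceeds the stated mandatory reporting window by about 60 days (59 to 62 by calendar month). The provisions agree during treatment and up to day 30.

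Three stronger conclusions might be drawn, and the documents do not support them:

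- The female difference is not fixed at 60 days, because the study period named in 5.6.6 may include follow-up.
- Partner notification is not in conflict between the sections when both are read as 3 months after the last dose. The partner difficulty lies between notification and reporting inside 7.2.5.
- The primary endpoint is not affected. Section 7.2.5 says that pregnancy is not itself an adverse event, and no planned summary or figure depends on these windows.

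The conclusion assumes that the period in 5.6.6 is the contraception period stated just before it. The protocol does not give the number of subjects of childbearing potential, or with partners of childbearing potential, so the number of affected pregnancies cannot be estimated. It is probably small.

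**What to change.** Reconcile 7.2.5 with 5.6.6 so that the notification windows agree and the mandatory reporting window covers every pregnancy that subjects are asked to notify. State whether the period in 5.6.6 includes the Follow-up Phase, and make clear whether the form-and-fax sentence in 7.2.5 is bound by the window before it. The length of the window is for the sponsor to settle; this review does not propose one.

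As a separate editorial correction, bring the first sentence of 5.6.6 into line with the rat embryo-fetal study in 1.3.2 and with the statement on fertility studies in 1.3.2.1.

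The cost is amendment wording and at most a few additional pregnancy reports.

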7.2.6 Other Malignancies

In addition to all routine AE reporting, all new malignant tumors including solid tumors, skin malignancies and hematologic malignancies are to be reported for the duration of study treatment and during any protocol-specified follow-up periods including post-progression follow-up for overall survival.

7.2.7 Eye-Related Adverse Events

New or worsening eye-related symptoms that are Grade 2 or higher, or a symptom that was Grade 2 or higher at baseline worsens, should be evaluated by an ophthalmologist whose findings should be reported on the ophthalmologic eCRF.

7.3 REPORTING OF SERIOUS ADVERSE EVENTS BY SPONSOR

Regulatory Authorities, Institutional Review Boards/ Independent Ethics Committees (IRBs/IECs), and Principal Investigators will be notified of SAEs in accordance with applicable requirements (eg, GCPs, ICH guidelines, national regulations, and local requirements).

Pharmacyclics has a Pharmacovigilance Committee that will review and evaluate accumulating safety data from the entire clinical study database PCI-32765 at appropriate intervals (e.g., quarterly) to identify new safety signals or increased frequency of events. This will include an aggregate review and comparison to the control group of SAEs that were deemed as "not suspected" of being associated with use of the study drug because they were likely to have been manifestations of underlying disease or that commonly occur in the patient population.

8.0 STATISTICAL CONSIDERATIONS

No formal statistical tests of hypotheses will be performed as this is an open-label, long-term extension study. This study will remain open as long as there are active studies of PCI-32765 with subjects who could be eligible for this protocol.

Demographic characteristics, laboratory parameters, concomitant therapy, and AE incidence rates will be summarized using descriptive statistics. PD and deaths will be presented using a listing. Documented responses will be provided in a listing. All subjects who receive at least 1 dose of study drug in study PCYC-1103-CA will be included in the safety and efficacy analyses. All available efficacy and safety data will be included in data listings and tabulations. No imputation of values for missing data will be performed. Subjects lost to follow-up will be included in statistical analyses to the point of their last evaluation. All study data will be examined using standard data management operating procedures.

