1.5 JUSTIFICATION OF STUDY DESIGN AND DOSE RATIONALE

This study is a long-term safety and efficacy extension study. It allows subjects meeting requirements for roll over from their parent protocol and who want to continue receiving study drug to continue on study drug. This reduces the burden of study visits and tests on the subjects and allows them to continue to have access to the investigational product.

The starting dose level for all subjects enrolled in this study will be based on the dose level the subject was receiving in the parent study. Study drug will be administered continuously without interruption. If the subject was in a weight-based dose cohort (subjects from PCYC-04753

study), then the fixed dose up to 840 mg/day that most closely approximates the weight-based dose will be chosen (refer to Section 5.4.2 for information on dose adjustments).

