3.3 OTHER ENDPOINTS

Other endpoints of this study are:

- Long-term tolerability as measured by treatment-related SAEs and discontinuation of study treatment due to AEs
- PD and death events
- Documented responses

4.0 SELECTION AND WITHDRAWAL OF SUBJECTS

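### Section 8.0 assigns progression, death and response to listings and names no time-adjusted summary, although follow-up is open-ended and unequal

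*Protocol*

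**What the plan says.** Protocol Section 3.3 names "PD and death events" and documented responses among the other endpoints, beside a tolerability endpoint based on adverse events (AEs). Section 1.5 states: "This study is a long-term safety and efficacy extension study".

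Section 8.0 tests no hypotheses. It lists what will be described statistically: "Demographic characteristics, laboratory parameters, concomitant therapy, and AE incidence rates will be summarized using descriptive statistics". PD, death and response are not in that sentence. They come next: "PD and deaths will be presented using a listing. Documented responses will be provided in a listing".

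The same paragraph then says "All subjects who receive at least 1 dose of study drug in study PCYC-1103-CA will be included in the safety and efficacy analyses" and "All available efficacy and safety data will be included in data listings and tabulations". Subjects lost to follow-up are included up to their last evaluation. The synopsis gives the population and the tabulation statement but not the two listing sentences.

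Follow-up is long and has no fixed end. Section 6.2.2 schedules CT from the first parent-study dose, Section 6.3.3 requires survival contact every 3 months until study end, and Section 3.1 keeps the study open while other studies could still feed it.

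**The concern.** The protocol collects dated progression and survival information for years and then names a listing as the specific presentation. Follow-up is staggered: some subjects will have been observed for months and others for many years when the data are cut. The number of deaths in a listing, or that number divided by N, mixes these lengths and does not refer to any stated time horizon.

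Death matters most, because long-term safety is the study's purpose. Under Section 7.2.1 the AE period closes 30 days after the last dose, and later serious events are reported only if considered related. A later death not considered related therefore reaches the data through survival follow-up, and no summary of that follow-up is named in Section 8.0. A reader who wants the long-term risk of death would have to work it out from the listing, and dividing by N would understate it at the longer horizons.

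**Working it through.** The protocol states no event count, event rate, sample size or estimate for these endpoints, so there is no planned figure to reproduce. The check has three parts.

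**1. What is named for each endpoint**

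| Endpoint (Section 3.3) | Presentation named in Section 8.0 |
|---|---|
| Treatment-related SAEs; discontinuation due to AEs | AE-based, so within the AE incidence summaries |
| PD and death | Listing; general promise of listings and tabulations |
| Documented responses | Listing; general promise of listings and tabulations |

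No rate at a time point, no interval and no time-to-event method is named for the last two rows.

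**2. Length of scheduled follow-up** (Section 6.2.2, 28-day cycles)

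- To cycle 18: 18 × 28 = 504 days, with 18 / 3 = 6 CTs.
- Cycles 18 to 36: to 36 × 28 = 1008 days (1008 / 365.25 = 2.76 years), with (36 − 18) / 6 = 3 more CTs.
- Thereafter: one CT every 12 × 28 = 336 days.

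After a complete response, scans are required only to confirm progression, so this is the fullest schedule.

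**3. Crude fraction against risk** (illustration; the inputs are assumptions)

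Assume a constant death hazard h per year and potential follow-up spread evenly over 0 to T years, with T = 5.

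- Expected crude fraction dead = 1 − (1 − exp(−hT)) / (hT)
- Risk of death by T = 1 − exp(−hT)

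For h = 0.08, hT = 0.40 and exp(−0.40) = 0.6703. The crude fraction is 1 − 0.3297 / 0.40 = 0.176, and the 5-year risk is 0.330.

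| Assumed hazard per year | Crude fraction dead | 5-year risk |
|---|---|---|
| 0.05 | 11.5% | 22.1% |
| 0.08 | 17.6% | 33.0% |
| 0.15 | 29.6% | 52.8% |

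The two columns measure different things. At h = 0.08 the crude fraction lies close to the risk at the mean potential follow-up of 2.5 years, 1 − exp(−0.20) = 18.1%. It is therefore a number without a stated horizon, and it is too low if read as the risk at the longest one. That direction holds for any positive hazard when potential follow-up is unequal.

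**The case against.** A reader might infer from the two listing sentences that listings are the only output and that the study can yield no estimate of these endpoints. The protocol does not support that. Section 8.0 never says only, it promises tabulations of all efficacy data, it defines a population for efficacy analyses, and nothing in it forbids an estimate. A statistical analysis plan, not available here, may define one. It would also be wrong to extend the point to every other endpoint, because the tolerability endpoint is covered by the AE summaries.

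Further points on the other side are fair:

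- The endpoints are worded as events and documented responses, not as progression-free survival, overall survival or a response rate. The only primary objective is safety, so listings fit the wording.
- Deaths within 30 days of the last dose must be reported as SAEs (Section 7.2.1) and so enter the AE summaries.
- The CTs are not wasted without an estimate. Progression is a reason to discontinue treatment (Section 4.3) and must be confirmed by CT (Section 6.2.2).
- The hazards and the follow-up spread in the illustration come from outside the protocol.

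All of this limits the point without removing it. The protocol is not silent here: it separates what is summarized from what is listed and puts PD, death and response on the listing side. A plain tabulation of counts, which is all the general sentence promises, has the same defect as a count taken from the listing. Reporting deaths within 30 days as SAEs does not cover later deaths not considered related.

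**Conclusion.** The point holds as a minor weakness in a stated method. Section 8.0 names listings for PD, death and response, leaves them out of the descriptive summaries, and is unclear about what its promised tabulations add for them. With open-ended and unequal follow-up, neither a listing nor a crude count over N gives an interpretable long-term risk of death or progression.

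The size cannot be derived from the protocol. The illustration puts the 5-year risk at about 1.8 to 1.9 times the crude fraction for hazards of 0.05 to 0.15 per year (22.1 / 11.5 = 1.92; 52.8 / 29.6 = 1.78), under a constant hazard and even follow-up over 0 to 5 years. It shows direction and does not predict this study's results. The primary safety endpoint is not affected.

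**What to change.** Keep the listings. Add to Section 8.0 that death, and PD or death, will also be summarized descriptively by Kaplan-Meier, by histology where numbers allow, with subjects censored at their last evaluation.

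State the time origin. Use the first parent-study dose, with delayed entry at the first PCYC-1103-CA dose, because subjects are in this study only if they reached rollover. Tumor baseline and CT timing already run from the parent study (Sections 6.2.1 and 6.2.2).

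Make one exception. PCYC-04753 subjects who enrolled after progression have a new tumor baseline (Section 6.2.1), and their earlier progression precedes entry, so PD or death timed from the first parent dose is undefined for them. Start their PD clock at the first PCYC-1103-CA dose and present them separately.

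The cost is a short addition to Section 8.0, two descriptive outputs, and linkage of first-dose dates from the parent studies. No new assessments are needed. If the sponsor does not want these summaries, Section 8.0 should say plainly that the endpoints are listed only and what the promised tabulations cover.
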